PMA	Premarket Approval
PN Q	Pediatric Nutrition Questionnaire
SAE	Serious Adverse Event/Serious Adverse Experience
SCAS	Spence Child Anxiety Scale Questionnaire
SD	Standard Deviation
SIRS	Systemic Inflammatory Response Syndrome
SOP	Standard Operating Procedure
TBWL	Total Body Weight Loss
UADE	Unanticipated Adverse Device Effect
US	Ultrasound
WMC	Weight Management Clinic

Study Summary

Title	Safety and Efficacy of Endoscopically Placed Intragastric Balloon in Obese Adolescents with Comorbidities – A Pilot Study
Running Title	IGB in Obese Adolescents with Comorbidities
IRB Protocol Number	15-009191
Phase	Pilot
Methodology	Open Label
Overall Study Duration	60-64 Weeks
Subject Participation Duration	12 months
Objectives	
 • Determine if placement of IGB for a period of 6 months is safe and results in weight loss with metabolic improvement in obese adolescents • Determine if IGB is well tolerated by adolescents • Determine if weight loss is sustainable after the IGB removal through integrating the subjects in the pediatric weight management program
Number of Subjects	12
Diagnosis and Main Inclusion Criteria	Subjects must have $\text{BMI} > 35 \text{ kg/m}^2$ with one severe comorbidity or $\text{BMI} > 40 \text{ kg/m}^2$ with two or more mild comorbidities
Study Device	Orbera Intragastric Balloon (Apollo Endosurgery Austin, TX)
Duration of Exposure	6 months
Statistical Methodology	The study results will be largely descriptive. Standard statistical analysis will be performed. Multiple linear and logistic regression analysis will be performed to determine significant variables relating to risk. A p-value of < 0.05 will be considered statistically significant.

1 Introduction

This document is a protocol for a human research study. This study will be carried out in accordance with the procedures described in this protocol, applicable United States government regulations and Mayo Clinic policies and procedures.

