1.5.3 Potential Benefits

The Orbera intragastric balloon is expected to result in 12.3%, 13.16 and 11.27% total body weight loss (TBWL) at 3, 6, and 12 months after implantation, respectively, based on recent review.[18] This balloon is currently FDA approved for use in adults in the United States. Other potential benefits include improving the metabolic syndrome manifestation such as:

1. Sustainable decrease in baseline heart rate (>10 beats/min) and systolic blood pressure (>10 mmHg/hg)
2. Normalization of liver function panel
3. Decrease in fatty liver infiltration on liver ultrasound (US)
4. Decrease in Hg1Ac level

5. Improvement of fasting lipid profile
6. Increase in activity level

2 Study Objectives

Primary Objective:

Assess the safety and effectiveness of an intragastric balloon device in obese adolescent subjects with comorbidities to assist with weight reduction and reverse metabolic complications.

The intended use for the subject device (IGB) in adolescents is to induce > 10% total body weight loss in morbidly obese adolescents.

Specific Aims:

- Determine if placement of IGB for a period of 6 months is safe and results in weight loss and metabolic improvement in obese adolescents
- Determine if intragastric balloon is well tolerated by adolescents
- Determine if weight loss is sustainable after the IGB removal through integrating the subjects in the pediatric weight management program

Study Protocol Hypothesis:

Intragastric balloon is a safe, well tolerated and effective intervention for weight loss and decreasing obesity complications in adolescents with comorbidities.

3 Study Design

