4.4 Early Withdrawal of Subjects

4.4.1 When and How to Withdraw Subjects

Subject will be withdrawn from the study:

- Subject safety issues, adverse device effects
- Failure of subject to adhere to protocol requirements
- Subject decision to withdraw from the study (withdrawal of consent)

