4-Female subjects will have a urine pregnancy test in the morning before the IGB insertion. Once the pregnancy test is confirmed negative, then the IGB can be inserted. At this visit, the subject will also be given a wallet card with emergency information, as well as Mayo Clinic brochures regarding the upper endoscopy and intragastric balloon for weight loss.

5-At the 6 month visit, the subject will have blood samples drawn; a physical exam by the pediatric endocrinologist ([name]) or a pediatric gastroenterologist ([name]); and a meeting in the weight management clinic with the dietitian. Following the blood samples, PE, and WMC, the IGB will be removed at the same visit. The 6 month visit and balloon removal may all be completed in one day, or they may be completed on separate days depending on scheduling times and the subject's availability. This will be up to the discretion of the study team. In order to prepare for the IGB removal, the subject will need to be on a liquid diet for 48 hours prior to its removal, and consume nothing by mouth for at least 12 hours prior to the IGB removal.

6-Other tests include:

- CBC with differential
- Electrolytes panel (Sodium, Potassium, Calcium, Creatinine, Chloride, Bicarbonate, BUN)
- Liver function tests (AST, ALT, Alkaline phosphatase, Total Bilirubin, Total Protein, Albumin)
- Nutritional assessment (Fe/TIBC, B12, Folic Acid, 25-Hydroxy Vitamin D, Ferritin)
- Coagulation panel (ProTime/INR, PTT)
- Total Cholesterol/Lipid panel

- Thyroid function tests, PTH
- Insulin
- Glucose
- CRP
- HgA1c
- Urine sample

7-Questionnaires will be given to the subject after consenting to complete at home with a request that they be returned at the baseline visit. The PN Q will be returned to and reviewed by the dietitian at the weight management clinic. The CES-D and SCAS will be returned to and reviewed by the psychologist during the subject's psychological assessment. Any elevations in the CES-D and SCAS surveys will be further assessed during the subject's visit with the psychologist. If clinically indicated, additional psychological assessment and follow-up that may be needed and will be part of the subject's standard of care.

8-At the PE, the subject's height, weight, waist circumference, HR, BP, and demographics will be collected at baseline, 3, 6, 9 , and 12 months.

7 Statistical Plan

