This is a pilot study of 12 subjects only, so results will be largely descriptive. Standard statistical analysis will be performed. We will use t-tests or alternative measures will be used to test whether weight loss was significant from baseline to each of the follow up points.

8 Safety and Adverse Events

All adverse events occurring during the study, including those not meeting the criteria of an Unanticipated Adverse Device Effect (UADE) will be recorded on the appropriate case report form. Records of these events will be maintained and reports submitted to the FDA and IRB according to the regulatory requirements. All adverse events will be reported. Expected clinical adverse events and anticipated adverse device effects are those listed in Section 1.5.2.

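### Separate t-tests at each visit rest on whoever is weighed that day; one mixed model on the scheduled weights would reduce the bias if poor responders leave, by how much depending on why they leave

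*Combined protocol and SAP*

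**What the plan says.** Section 7 sets the scope: "This is a pilot study of 12 subjects only, so results will be largely descriptive". The only efficacy method it names is t-tests, or unspecified alternatives, "to test whether weight loss was significant from baseline to each of the follow up points". The Study Summary adds a threshold: "A p-value of < 0.05 will be considered statistically significant". There is no repeated-measures model, analysis set, missing-data rule or expected dropout rate.

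Weights are scheduled in Table 2, footnote 8: "the subject's height, weight, waist circumference, HR, BP, and demographics will be collected at baseline, 3, 6, 9 , and 12 months". The balloon comes out at month 6, so months 9 and 12 fall after removal. Those two visits serve the third specific aim in Section 2: "Determine if weight loss is sustainable after the IGB removal".

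The withdrawal reasons in Section 4.4.1 include "Failure of subject to adhere to protocol requirements", besides safety and withdrawn consent. Section 4.4.2 has weight collected for withdrawn subjects only until the balloon is removed. The six months of follow-up after that are clinical and for safety.

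The effect sizes come from Section 1.5.3: "The Orbera intragastric balloon is expected to result in 12.3%, 13.16 and 11.27% total body weight loss (TBWL) at 3, 6, and 12 months". No SD, within-subject correlation or month-9 value is given.

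**The concern.** A paired t-test at a given month needs a baseline weight and a weight at that month. If subjects leave, the four tests describe different groups, and the later groups are those who stayed. The earlier weights of those who left are then ignored, although they carry information about what is missing.

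In a programme built on diet and lifestyle, non-adherence may go with poor weight loss. If it does, the later means run high and the fall between months 6 and 12 looks smaller than it is. A descriptive study of 12 subjects has the estimated mean as its main product, so the size of that mean is what is at stake.

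**Working it through.** The plan states no power, dropout or bias figure, so there is none to reproduce. The question is how large the bias could be.

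**Inputs from the documents.** N = 12. Mean loss is 12.3, 13.16 and 11.27% at months 3, 6 and 12. Implied regain is 13.16 − 11.27 = 1.89 points.

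**Assumptions.** Month-9 mean 12.2%; SD 6 or 8 points; correlation between visits 0.6 or 0.8. All subjects are seen at month 3. A subject below 10% loss at a visit leaves afterwards with probability 0.25 or 0.5. This makes eight scenarios, with on average 2.6 to 4.9 of 12 missing at month 12.

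**Hand check.** If a fraction m is missing and attenders lose D points more than leavers, the attender mean is too high by m × D. With 3 missing and D = 4: 3/12 × 4 = 1.0. With 5 missing and D = 9: 5/12 × 9 = 3.75.

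**Simulation, dropout following recorded weights** (1,500 trials per scenario):

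| Month-12 mean, points | Attenders only | Random-intercept model |
|---|---|---|
| Bias | +0.97 to +3.65 | −0.03 to +0.14 |
| Root mean squared error | 2.14 to 4.45 | 1.77 to 2.92 |

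A repeat run gave +0.9 to +3.6 against −0.2 to +0.2.

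**Dropout following the unseen weight**, same settings otherwise: +1.5 to +4.0 for attenders only, +0.4 to +1.7 for the model. The model had the lower root mean squared error in all 16 settings.

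**Covariance not as assumed, dropout still following recorded weights.** If correlation decays over time (AR(1)), the model's bias is −0.6 to −0.1. If the SD rises from 4 to 9 points over follow-up, +0.7 to +2.0 remains, and the model removes about half of the bias or less.

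**Regain.** The month-6 attender mean is inflated too, by 0.4 to 1.5 points, so only the difference in bias counts. That net bias is 0.6 to 2.1 points. Apparent regain is 1.89 minus the net bias: about 0.2 to 1.1 points in seven of the eight recorded-weight scenarios (0.14 to 1.26 in a larger run of 6,000 trials each). It vanishes (−0.20) only at SD 8, correlation 0.8 and leaving probability 0.5.

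**Check in kilograms.** Assume baseline 120 kg (SD 20), SD of loss 8 points, correlation between adjacent visits 0.6 to 0.9, and a smooth dropout curve. On a true month-12 loss of about 13.5 kg:
- Dropout on recorded weights: attenders only +1.7 to +3.0 kg; random intercept −0.2 to +1.1 kg.
- Dropout on unseen weights: attenders only +2.5 to +3.5 kg; random intercept +1.6 to +2.1 kg.
- Dropout unrelated to response (checked at N = 400): −0.2 kg for attenders only, so no material bias.
- An unstructured covariance could not be fitted in about 5 to 19% of trials with 12 subjects.

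**Complete data.** Visit means agree under every covariance structure. Standard errors need not: in one simulated data set the month-12 value was 2.22 kg for the paired t-test and 2.69 kg for the random intercept.

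**Significance.** With all 12 subjects and SD 8, the noncentrality is 13.16 / (8/√12) = 5.70, giving two-sided power 0.999. With SD 12 it is 3.80, giving 0.93. Whether weight falls is hardly in doubt; how much is.

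**The case against.** Selective dropout is nowhere stated. None of the withdrawal reasons in Section 4.4.1 is a weight-loss rule, no dropout rate is given, and if leaving is unrelated to response there is nothing to correct. Section 7 does not say that only attenders are analysed, and its open wording about alternatives does not rule out a mixed model. All of this stands. It makes the bias conditional, but the plan still commits to no method that would guard against it.

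A reader might infer that the bias can hide all of the regain, since 1 to 4 points exceeds 1.89. That compares the month-12 bias alone with a difference between two visits. Once month-6 inflation is counted, regain disappears in one of eight scenarios. Moreover, the paired month 6-to-12 change among completers was 2.0 to 2.45 points against a true 1.89, so that contrast does not hide it. Section 7, however, plans only comparisons with baseline.

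A reader might also infer that the mixed model settles the matter and changes nothing when nobody is missing. The near-zero bias holds only when dropout follows recorded weights and the covariance is adequate. Regain after removal followed by a missed visit would break the first condition. The second part is true of means but not of standard errors or p-values. A subject with no weight from month 3 onward, for example after early removal for intolerance, adds nothing to a model of percentage change.

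**Conclusion.** The concern holds in conditional form. By default the planned tests use whoever is weighed, and later weights of withdrawn subjects are not collected as study data. If poor responders leave, the month-12 mean is overstated by about 1 to 4 points. A comparison of attender means then understates regain, in most scenarios without erasing it. The mixed model removes nearly all of the bias in the favourable case and part of it otherwise.

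The sizes rest on the assumed SD, correlation, month-9 mean and dropout rule. The pattern is firmer than any single figure. The 1.89-point regain is the difference between two pooled estimates (Section 1.4 gives 8.17 to 14.36% as the 95% interval at 12 months), so it is a benchmark and not a forecast. The documents do not support saying that later results will be biased or that the significance tests will mislead. This is a cheap improvement.

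**What to change.** In Section 7:

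- Estimate mean percentage weight change at months 3, 6, 9 and 12 with one linear mixed model: visit as a categorical fixed effect, a random subject intercept, REML and Kenward-Roger degrees of freedom. An unstructured covariance is too fragile for 12 subjects.
- Estimate the month 6-to-12 change from the same model for the sustainability aim.
- Report 95% confidence intervals and the number observed at each visit. List subjects with no weight from month 3 onward.
- Keep the paired t-tests as supportive.
- Add one sensitivity analysis for dropout that depends on unseen weights. One form lowers the predicted loss of missing subjects by a fixed amount chosen in advance; with 4 of 12 missing and 3 points, the mean falls by 4/12 × 3 = 1.0 point.

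Using any weights recorded in the clinical follow-up after early removal would also reduce the missingness itself.

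The cost is a paragraph of SAP text and a few lines of code on weights already scheduled. The small downsides are an assumed covariance structure and, even with complete data, standard errors and p-values that can differ from the paired t-test. The change does not address the binary primary endpoint of at least 10% loss, which needs its own rule for missing subjects.

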3.2 Primary Study Endpoints

The primary endpoint will be achieving $\geq 10\%$ total body weight loss (TBWL).

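### The one analysis specified in Section 7 tests weight loss against zero; it does not address the primary endpoint of at least 10% total body weight loss and answers the sustainability aim only in part

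*Combined protocol and SAP*

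**What the plan says.** - **Primary endpoint (Section 3.2).** "The primary endpoint will be achieving" at least 10% TBWL. No visit, denominator or summary measure is attached. Section 2 gives the device's intended use as to "induce > 10% total body weight loss in morbidly obese adolescents".
- **Aims (Section 2).** One aim is to "Determine if placement of IGB for a period of 6 months is safe and results in weight loss and metabolic improvement in obese adolescents". Another is to "Determine if weight loss is sustainable after the IGB removal".
- **Analysis (Section 7).** "This is a pilot study of 12 subjects only, so results will be largely descriptive". Beyond an undefined standard analysis, the only method given is t-tests, or unnamed alternatives, to "test whether weight loss was significant from baseline to each of the follow up points".
- **Study Summary.** It sets p < 0.05 and adds: "Multiple linear and logistic regression analysis will be performed to determine significant variables relating to risk". This is not tied to the 10% endpoint and is not repeated in Section 7.
- **Expected effect (Section 1.5.3).** The balloon "is expected to result in 12.3%, 13.16 and 11.27% total body weight loss (TBWL) at 3, 6, and 12 months after implantation". These are pooled review figures; Section 1.4 notes that adolescent data are scarce.
- **Weights.** Section 5.4 and footnote 8 of Table 2 schedule weight at baseline and months 3, 6, 9 and 12. Section 5.4 keeps all subjects under the weight management team after removal.
- **Withdrawal (Section 4.4.2).** For subjects withdrawn for reasons other than severe adverse events, weight is collected until the balloon is out. The same paragraph then plans six more months of clinical follow-up.

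**The concern.** The test and the endpoint ask different questions. A test of loss from baseline has an implied null of zero mean change. The endpoint asks how many subjects cross a 10% threshold. A small p-value could therefore be reported as the efficacy result when few subjects had reached the target.

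The sustainability aim has a similar gap. Tests at months 9 and 12 against baseline show whether some net loss remains. They do not show how much of the loss achieved with the balloon in place was kept after removal.

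The denominator and the handling of missing month-6 weights are also unwritten. In an open-label study of 12, settling them after the results are seen can change the reported responder rate.

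**Working it through.** The documents contain no power calculation, SD or expected responder rate, so there is no plan figure to reproduce. The inputs are n = 12 (Study Summary, Section 7), alpha 0.05 (Study Summary; two-sided assumed), the 10% threshold (Section 3.2), and mean losses of 13.16% at month 6 and 11.27% at month 12 (Section 1.5.3). The SD of %TBWL is assumed to be 5, 7 or 10 points, with normal losses.

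**1. Smallest significant mean loss.** The test against zero is significant when mean > t(0.975, 11) × SD / √12 = 2.201 / 3.464 × SD = 0.635 SD.

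| Assumed SD | Smallest significant mean | Share of subjects at ≥10% if that were the true mean |
|---|---|---|
| 5 | 3.2% | Φ((3.18 − 10)/5) = 9% |
| 7 | 4.4% | Φ((4.45 − 10)/7) = 21% |
| 10 | 6.4% | Φ((6.35 − 10)/10) = 36% |

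**2. Probability of significance against zero (noncentral t, n = 12).**

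| True mean | SD 5 | SD 7 | SD 10 |
|---|---|---|---|
| 5% (assumed) | 88% | 62% | 35% |
| 10% (half of subjects below target) | >99.9% | 99% | 88% |
| 13.16% (cited, month 6) | >99.9% | >99.9% | 98.5% |

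The test hardly separates a true mean on the threshold from the cited mean above it.

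**3. An interval read against 10%.** At a true mean of 13.16%, the lower 95% limit for the mean exceeds 10% with probability 51%, 30% or 17% (SD 5, 7, 10). This addresses the target, though 12 subjects will often not settle it.

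**4. Sustainability.** Suppose mean loss falls from 13.16% at month 6 to 6% at month 12, with SD 8 at month 12 (hypothetical). Against baseline, t = 6 / (8/√12) = 2.60 and p = 0.025, still significant. Yet (13.16 − 6)/13.16 = 54% of the loss has been regained.

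**5. What a paired month 6-to-12 comparison could show.** The SD of change is SD × √(2(1 − ρ)), with ρ assumed to be 0.6 to 0.8. The 95% half-width is 0.635 times that:
- SD 5, ρ 0.8: 0.635 × 3.16 = 2.0 points.
- SD 10, ρ 0.6: 0.635 × 8.94 = 5.7 points.

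The change implied by the cited means is 13.16 − 11.27 = 1.89 points. The interval would exclude zero for that change with probability 47% in the first case and 10% in the second. For a regain of half the month-6 loss (6.58 points, assumed), the probabilities are >99% and 64%.

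**6. Denominator.** Suppose 8 subjects respond and 2 of the 12 have no month-6 weight. Observed cases give 8/10 = 80% (exact 95% CI 44% to 97%). All implanted subjects give 8/12 = 67% (35% to 90%).

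**The case against.** The strongest reply is that this is a single-arm, 12-subject pilot declared largely descriptive, that a responder count fits that description, and that month 6 is plain from the 6-month exposure, the first aim and the weight taken at removal. Much of this stands. No powered test is needed, and month 6 is strongly implied. But the count is not written, Section 7 treats all follow-up points alike, and the one test it does name addresses another question.

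Four stronger readings are tempting and are not supported:

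- **That significance against zero is near certain whether or not the target is met.** Step 2 contradicts this: at a true mean of 5%, the probability is only 35% with SD 10. What holds is that significance can occur well below 10%.
- **That weights stop after any early balloon removal.** Section 4.4.2 concerns subjects withdrawn for reasons other than severe adverse events. Removal for intolerance or under Section 6.4 is not stated to be withdrawal, and Section 5.4 keeps all subjects in follow-up.
- **That the two thresholds set rival endpoints.** Section 2 states an intended use, and its strict inequality differs from Section 3.2 only for a loss of exactly 10%. This is clerical.
- **That sustainability is left unanalysed.** The month-9 and month-12 tests do show whether net loss persists, which is part of the answer. The paired comparison adds the amount retained, with limited precision.

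**Conclusion.** The point holds as a mismatch between the specified analysis and the primary endpoint, and should be fixed. The test against zero can be significant at mean losses just above 3.2%, 4.4% or 6.4%, so it cannot stand in for a 10% target. A significant month-12 result can hide regain of more than half the month-6 loss.

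The thresholds rest on assumed SDs of 5 to 10 points and a two-sided 5% level. The responder shares and probabilities also assume normal losses, and those at 13.16% borrow a pooled review figure that may not carry over to adolescents. The mismatch itself rests on the text alone.

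A reader might infer that the trial cannot assess its primary endpoint. The documents do not support that: the weights needed are already scheduled, and what is missing is the written analysis.

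**What to change.** In Sections 3.2 and 7:

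1. Name the 6-month removal visit as the primary time point.
2. Report the number and proportion of all implanted subjects with at least 10% TBWL at that visit, with an exact 95% CI. Count subjects without a month-6 weight as non-responders and show observed cases alongside.
3. Report mean %TBWL at 6 months with a 95% CI read against 10%.
4. For sustainability, add the paired month 6-to-12 change with a 95% CI and the number of pairs, and the number still at 10% or more at month 12.
5. Keep the tests against baseline as supportive.
6. Use one form of the 10% threshold in Sections 2 and 3.2.

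Reconcile the sentence in Section 4.4.2 on weight collection with that section's own six further months of follow-up and with Section 5.4, so that it is clear whether a month-6 weight is recorded after withdrawal.

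The cost is mostly wording, since the visits and weights are already planned. There are three downsides. Intervals will be wide (8/12 = 67%, 35% to 90%). Counting missing weights as non-response gives a conservative estimate, hence the observed cases alongside. The paired interval could show a large regain but probably not the 1.89-point change implied by the cited figures.
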